#### 3.2. Required Equipment

All data collection devices and the SUT will be identical in design and function and will be returned to the Sponsor at the end of the evaluation.

##### 3.2.1. Sponsor-provided

The Sponsor will provide the study sites with:

- Data collection device (DCD) for single-lead ECG collection
- Hardware to view single-lead ECG waveforms during data collection
- Assortment of other devices for simulation
  - a) Commercially available wrist-worn device [REDACTED]
  - b) Commercially available handheld device [REDACTED] and

companion device (tablet/phone/iPod)

### **3.2.2. Contract Research Organization (CRO)-provided**

The CRO will provide:

- 12-lead ECG monitor: GE Healthcare CardioSoft System. CardioSoft is a FDA cleared ECG device (K031561).
- Secure Network Attached Storage (NAS)

Investigational Study Site - provided

- Space to screen subjects
- Space to conduct testing and regular exam room/office equipment
- Equipment to record vital signs
- Appropriate safe and storage area for devices

### **3.3. Qualification Criteria for ECG Operators and Independent Cardiologists**

Only individuals trained by the Sponsor or its designee(s) will be qualified to assume the role of an ECG operator or independent cardiology reviewer. ECG operators may include appropriately trained technicians, students, nurses, and/or physicians. Cardiac technicians must be Certified Cardiographic Technicians. Cardiology reviewers may include physicians experienced in reading ECG leads in order to make diagnostic determinations of adult patients. Cardiology reviewers must be a licensed medical doctor specialized in cardiology.

Information regarding the specific training, years of experience, and specialty of each reviewer will be collected.

### **3.4. Randomization and Blinding**

This study is not randomized.

Cardiac technicians will be blinded in Part A and will not know which strip is the reference vs SUT strip.

U.S. board-certified cardiologists in Part B-1 and board-certified in Part B-2 will be blinded to the subject's past medical history and algorithm classification.

### **3.5. Duration of Subject Participation**

Subjects will participate in a screening visit and, if eligible, participate in the study at the same visit. Participants with AF who are not in AF at the time of screening will be eligible for re-screening and participation at a later date.

## **4. STUDY POPULATION**

### **4.1. Number of Subjects and Subject Recruitment**

Subject recruitment can be accomplished in any appropriate fashion, within the guidelines of the central Institutional Review Board (IRB).

### **4.2. Study Cohorts and Target Population**

The study will include 2 cohorts:

- A minimum of 260 subjects (up to a maximum of 400 subjects) with AF
  - A population of subjects with a known diagnosis of AF (permanent or persistent AF as the likelihood of being in AF during data collection is higher)
- Approximately 300 subjects with SR
  - A population of subjects with no known diagnosis of AF
- There is no age distribution requirement for the AF population. For subjects with SR, there will be at least 25 subjects in each of the 22-30, 31-50, 51-64 categories and at least 150 subjects in the 65+ category.
- Men and women should be equally represented between the two study cohorts with a goal of having women represent >30% of subjects.

### **4.3. Inclusion Criteria**

Subjects must meet all the following inclusion criteria to be enrolled:

1. Able to read, understand, and provide written informed consent
2. Willing and able to participate in the study procedures as described in the consent form
3. Individuals who are 22 years of age and older
4. Able to communicate effectively with and follow instructions from the study staff
5. Have a wrist circumference between 130 mm and 245 mm (measured at “band center” on the preferred wrist. This location is determined by asking the volunteer to put on a normal wrist-watch and marking the skin with a pen/marker to outline the edges of the band.)
6. For subjects enrolled into the AF population, subjects must have a known diagnosis of AF and be in AF at the time of screening. Subjects may have any type of AF including paroxysmal, persistent, and permanent AF although persistent and permanent AF are preferred as they are more likely to be in AF at the time of screening.

### **4.4. Exclusion Criteria**

Subjects who meet any of the following criteria may not be enrolled:

1. Physical disability that precludes safe and adequate testing
2. Mental impairment resulting in limited ability to cooperate

3. Subjects with a pacemaker or implantable cardioverter-defibrillator (ICD)
4. Acute myocardial infarction (MI) within 90 days of screening or other cardiovascular disease that, in the opinion of the Investigator, increases the risk to the subject or renders data uninterpretable (e.g., recent or ongoing unstable angina, significant valvular heart disease or heart failure, myocarditis or pericarditis)
5. Acute pulmonary embolism, pulmonary infarction, or deep vein thrombosis within 90 days of screening
6. Stroke or transient ischemic attack within 90 days of screening
7. Subjects taking rhythm control drugs (e.g., disopyramide, quinidine, flecainide, propafenone, amiodarone, dofetilide, dronedarone, sotalol, procainamide, ibutilide, moricizine, procainamide). An exception will be made for subjects who are undergoing scheduled cardioversion for known AF within 30 days after study participation. These study participants will be allowed to participate in the study even when on rhythm control drugs.
  - a. Rate control and anticoagulants, anti-platelet medications are permitted (e.g., metoprolol, atenolol, diltiazem, coumadin, clopidogrel, aspirin)
8. Symptomatic (or active) allergic skin reactions such as eczema, rosacea, impetigo, dermatomyositis or allergic contact dermatitis on both wrists or over electrode attachment sites including known allergy or sensitivity to fluoroelastomer bands primarily used in wrist worn fitness devices
9. Known sensitivity to medical adhesives, isopropyl alcohol, watch bands, or electrocardiogram (ECG) electrodes
10. A history of abnormal life-threatening rhythms as determined by the investigator (e.g., ventricular tachycardia, ventricular fibrillation, 3rd-degree heart block, resting heart rate < 50 bpm, resting heart rate >110 bpm)
11. Significant tremor that prevents subject from being able to hold still
12. Pregnant women: Women who are pregnant at the time of study participation.
13. [REDACTED]
14. [REDACTED]
15. For subjects enrolled into the sinus rhythm population, they must not have any diagnosis of AF. For example, subjects cannot be enrolled into the sinus rhythm population if they have a diagnosis of paroxysmal AF but during screening are in sinus rhythm.

#### **4.5. Subject Withdrawal and Replacement**

A consented, enrolled subject may withdraw from the study for any reason. Subjects who withdraw prior to participation or who fail to complete study participation will be replaced.

#### **4.6. Subject Follow up**

After completion of study participation, the subject is discharged from the study with no protocol-specified follow up.

## 5. STUDY PROCEDURES

### 5.1. Screening

Informed consent will be obtained before any study protocol-directed procedures are performed. After the signing of informed consent, the subject will be evaluated for eligibility according to the study inclusion/exclusion criteria (Section 4.3 and Section 4.4).

During screening, the following should be obtained on each subject

- Age
- Gender
- Race and ethnicity
- Occupation
- Diagnosed medical conditions
- Medications
- Allergies
- Smoking history
- Alcohol Use (self reported)
- Recreational Drug Use (self reported)
- Brief physical exam
- Height and weight
- Body mass index (BMI)
- Vital signs will be collected after sitting for at least 5 minutes (blood pressure with systolic recorded within the range of 80-180 mm Hg and diastolic recorded in the range of 40-120 mmHg, heart rate recorded within the range from 50-110 beats per minute, temperature recorded within range of 35.5-37.5 degrees)
- Urine Pregnancy testing for women of childbearing potential
- Caffeine intake
- Exercise habits
- Dominant hand
- Wrist circumference (for wrist that device will be worn on)
- Skin fold thickness (for wrist that device will be worn on)
- Wrist hairiness (for wrist that device will be worn on)
- 12-lead ECG will be collected supine after lying for at least 5 minutes

All volunteers will undergo a 12-lead ECG. The 12-lead ECG will be reviewed live by study personnel. AF subjects must be in AF at the time of the 12-lead ECG in order to be assigned to the AF population. If subjects are not in AF at the time of the 12-lead screening ECG, they may be re-screened for participation at a later date.

If any of the study staff believe the vital signs or screening 12-lead ECG are of poor quality, they may repeat the measurements.

## **5.2. Day of Participation**

Subjects will report to the clinic for evaluation at their scheduled date and time. No special preparation for this visit is required. All subjects may take their normal medications on the day of the study and may eat normally the day of participation. Participants will be asked to remove jewelry and any underwire bras during active data collection. It is recommended that participants wear t-shirt and shorts during data collection.

### **5.2.1. Study Procedures**

#### **5.2.1.1. Data Collection Device Set up**

The following procedures will be performed for each study subject at study participation:

1. Hand subject a watch (regular wristwatch) and ask subject to place it on his/her preferred wrist. Observe how the subject places the watch on their wrist.
2. Assign a device to each subject and document the device number.
3. Instruct the subject to choose his/her preferred wrist to wear the data collection device (DCD). The DCD can be worn on whichever side the subject prefers unless there is a skin condition on one wrist as noted above in the exclusion criteria, in which case, the device must be worn on the non-affected wrist. Record the subject's choice of wrist. If the subject does not have a side preference or skin condition on one wrist, the device will be placed on the left wrist.
4. Study staff will place the DCD on the study participant's wrist (as indicated in 3.). The device should be fitted tightly enough that it does not move when the hand/wrist is shaken.
5. Check band tightness for a snug fit and adjust as needed.
6. Instruct the subject to read the provided instructions on how to record a single-lead ECG. The written instructions are:
  - a) "It takes 30 seconds to record a measurement. It's important to keep your arms still. Try resting them on a table or your leg. To begin recording rest your finger on the knob."
  - b) Practice data will be recorded.
7. After the first practice run, site study staff will guide subject to appropriate study posture and grip (if not achieved independently during the first test run).

8. Allow subject up to three additional practice runs if more practice runs are needed to ensure study posture and grip instruction understanding (fewer than 3 additional practice runs are acceptable if study posture and grip are correct and subject is comfortable with the positioning),
9. Record the number of practice runs completed by the subject. First practice run data and number of practice runs completed by the subject will be used to determine ease of use.

#### 5.2.1.2. Data Collection

10. Instruct subject to remain seated for a 5-minute resting period prior to collecting three 12-lead ECGs and set the reference system to 40 Hz filter. Use standard placement of all 12-lead electrodes (with limb lead for Lead 1).
11. Collect 3 separate complete 12-lead ECGs (review to ensure there is no artifact). Each recording will be approximately 30 seconds in duration with a 1-minute rest period between each recording (i.e., 1 minute between the end of the previous recording and the start of the next recording). Simultaneously, instruct the subject to record 3 separate complete single-lead ECGs using the DCD. A total of three complete single-lead ECGs will be collected for each subject. Each recording will correspond to the time of collection of each 12-lead ECG recording.
  - c) Monitor the 12-lead waveform to ensure a good quality recording is obtained.
  - d) Monitor the waveform from the Lead 1 ECG from the DCD, between ECG recordings, provide feedback to the subject on how to improve the reading.
12. After data collection, instruct study subjects to rate the ease of use of the DCD on a scale of 1-5 (1 being Unable to Use, 2 being Below Average Ease of Use, 3 being Average Ease of Use, 4 being Above Average Ease of Use, 5 being Easiest to Use). Record the rating in the eCRF. Remove DCD from subject.
13. Instruct study subjects to apply and simulate a recording with each of the other devices [REDACTED] to rate the comfort and ease of use of each of these devices on a scale of 1-5 (Scale is listed above under #10). Record the ratings.

#### 5.2.1.3. Data Processing

14. The Sponsor will receive data files from:
  - a) The reference device 12-lead ECG files
  - b) Raw data DCD files
15. The Sponsor will check data for Protocol and MOP adherence.
16. For Part A (described below), the Sponsor will sync Lead 1 of the 12-lead (reference strip) to the corresponding SUT's strip to ensure that the same beats from each subject are presented.

17. The Sponsor will provide a portable document format (PDF) of the full 30-second strip of both the reference strips and the SUT's strips on the standard clinical ECG scale to Cardiac Core Lab (for both Part A, Part B-1, and Part B-2).
18. Cardiac Core Lab will print the strips for analysis and distribute to appropriate experts for review.

#### **5.2.1.4. Data Review by Cardiac Core Lab** (refer to Operations Plan/ Imaging Charter)

##### **19. Part A** (To address Objective 2a): Analysis of paired sets of strips.

- a) The Sponsor will prepare one paired set of strips from approximately 140 randomly selected subjects (70 AF, 70 SR) (approximate strips = 280 strips)
  - i. One set includes a Lead 1 strip from the 12-lead and a paired strip from the SUT.
  - ii. The first reading from data collection will be used for all subjects.
- b) Cardiac Core Lab review:
  - i. Three blinded, independent cardiac technicians will review each paired set of strips. The strips will be rendered semi-transparent through the use of back lighting and overlaid to visually assess for morphological similarity.
  - ii. One reviewer will identify the first six consecutive distinct readable PQRST complexes without artifact that match between the strips for evaluation. For example, if the reference strip has an artifact in beats 2 and 5 but all other beats are good and the strip from the SUT has artifact in beats 1 and 6 but all other beats are good, the six consecutive beats to be used will begin at beat 7 of both strips. The strip will be excluded if six consecutive beats cannot be found. The six PQRST complexes identified by the initial reviewer will be used by the 2 other reviewers.
  - iii. Each reviewer will assign a pass/fail to the strips by visually assessing all 6 PQRST complexes. A "pass" is given when the morphology of the PQRST complexes appears to overlay to the unaided eye.
  - iv. Measure R amplitude from the isoelectric baseline to the nearest millimeter for the first two QRS complexes in both the reference strip and SUT strip. The reviewers will be blinded to the identity of the reference strip and SUT strip. Record these lengths.

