#### 5.3.2. Secondary Objectives/Endpoints

Two hypotheses associated with secondary objective 2a to demonstrate that the SUT produces a waveform that provides clinically equivalent information to the gold standard Reference will also be tested.

The first hypothesis is aimed at demonstrating that the proportion of subjects with a pass rating based on the visual assessment of 6 consecutive readable PQRST complexes is at least 80%.

The majority result from the pass/fail readings of the three independent cardiac technicians will be used for analysis. The hypothesis for this objective can be stated as follows:

$$H_{03}: \Pi_1 = 0.80$$

vs.

$$H_{A3}: \Pi_1 > 0.80$$

where  $\Pi_1$  represents the true population subject success proportion of pass ratings.

The second hypothesis associated with objective 2a is based on the results of the quantitative analysis of the R-wave amplitudes as measured by each of three cardiac technicians on the paired SUT and Reference strips in Part A. The majority result from the three technicians (i.e., if at least two technicians measure the difference in amplitudes between the SUT and reference strip to be  $\leq 2$ mm, then the paired strips for a given subject will be deemed  $\leq 2$ mm) will be used for testing the hypothesis that the proportion of paired R-Wave amplitude measurements  $\leq 2$  mm of each other is at least 80%

$$H_{04}: \Pi_2 = 0.80$$

vs.

$H_{A4}: \Pi_2 > 0.80$

where  $\Pi_2$  represents the true population agreement proportion of paired R-Wave amplitude measurements. For each participant, the QRS complex from the 12-lead ECG with the largest R amplitude (out of the two QRS complexes with R-wave amplitude measurements will be used for purposes of determining the majority result.

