### 5.3.3 Sample Size

Under the assumption that the true population sensitivity is 95%, 231 subjects who are diagnosed with AF based on the 12-lead ECG reference strip and where the device algorithm classification produces a result of AF or SR will provide at least 80% power to reject its null hypothesis,  $H_{01}$ , using a one-sided type I error of 0.025. Moreover, under the assumption that the true population specificity is 96.5%, 226 subjects who are diagnosed with SR based on the 12-lead ECG reference strip and where the device algorithm classification produces a result of AF or SR will provide at least 80% power to reject its null hypothesis,  $H_{02}$ , using a one-sided type I error of 0.025. To account for obtaining readable waveforms, a minimum of 260 subjects with a known diagnosis of AF and approximately 300 subjects with no known diagnosis of AF will be enrolled. The sample size for AF subjects may be increased if the unreadable/unclassifiable rate is higher than originally assumed up to a maximum of 400 enrolled AF subjects.

For the secondary objective hypothesis,  $H_{03}$ , under the assumption that the true population subject success rate is 90%, 88 subjects will provide at least 80% power to reject its null hypothesis using a one-sided type I error of 0.05. To account for obtaining readable waveforms, approximately 140 subjects (70 SR; 70 AF) will be randomly selected.

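### Part A does not stop the voting technician who picks the six beats from skipping beats because their shape differs, so H03 may be scored on beats chosen partly on its own outcome

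*Combined protocol and SAP*

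**What the plan says.** Part A (protocol section 5.2.1.4, item 19, repeated in the synopsis) supports secondary objective 2a. Item 19b(i) describes the reading: the two strips are back-lit and overlaid so that their morphology can be compared. Item 19b(ii) fixes the beats: "One reviewer will identify the first six consecutive distinct readable PQRST complexes without artifact that match between the strips for evaluation". It also says: "The six PQRST complexes identified by the initial reviewer will be used by the 2 other reviewers". Under item 19b(iii) all three technicians, including the one who chose the beats, vote pass or fail. A pass "is given when the morphology of the PQRST complexes appears to overlay to the unaided eye". A pair in which six such beats cannot be found is excluded, not failed.

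The worked example in item 19b(ii) turns only on artifact in either strip, and concludes that "the six consecutive beats to be used will begin at beat 7 of both strips". Under item 16 the sponsor first synchronises the strips so that they show the same beats. Section 5.3.9 restates the exclusion in terms of paired beats. Sections 3.1 and 5.3.2 describe the scored beats only as readable.

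Section 5.3.2 takes the majority of the three votes and sets H03 to show that "the proportion of subjects with a pass rating based on the visual assessment of 6 consecutive readable PQRST complexes is at least 80" per cent. Sections 3.4 and 5.3.4 blind the technicians to which strip is the reference and which comes from the software.

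**The concern.** H03 asks whether the software's beats have the same shape as the reference beats. The result is credible only if the beats are chosen without regard to how well they overlay. Item 19b(ii) does not secure this, for four reasons.

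- The condition that the beats match is undefined. Read as shape, it overlaps the pass criterion.
- Even if it means the same beat in time, no rule says what to do with a readable beat whose shape differs between strips. That is the case H03 exists to detect, and the example covers only beats already labelled as artifact.
- Nothing requires the beats to be chosen before the strips are overlaid. The picker can see the disagreement while deciding what counts as artifact.
- The picker also votes, and the other two technicians have no other window to score.

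If some distorted beats are passed over instead of being scored, the observed pass rate rises above the rate for unselected beats and the one-sided 0.05 error rate no longer holds.

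**Working it through.** **1. The plan's own figure.** Section 5.3.3 assumes a null of 0.80 and a true rate of 0.90, and states that "88 subjects will provide at least 80% power to reject its null hypothesis using a one-sided type I error of 0.05". With an exact binomial test on 88 pairs, H03 is rejected at 77 or more passes:
- P(X ≥ 77 | n = 88, p = 0.80) = 0.046
- P(X ≥ 77 | n = 88, p = 0.90) = 0.833

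The stated sample size is confirmed. The issue is which beats enter the test.

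**2. Model for skipping.** This is an assumption, since the documents give no per-beat rates. Each beat is distorted independently with probability q, and a distorted beat is passed over as artifact with probability s. The window is the first six consecutive beats not passed over, and the pair passes if all six are undistorted.

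To place the device exactly at the null for an unselected window:

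(1 − q)^6 = 0.80, so q = 1 − 0.80^(1/6) = 0.0365.

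A beat that is not passed over is undistorted with probability (1 − q)/(1 − qs). The pass rate among analysed pairs is therefore

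[(1 − q)/(1 − qs)]^6 = 0.80/(1 − qs)^6.

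**3. Results with 88 pairs, rejecting at 77 or more.**

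| Share s of distorted beats skipped | qs | (1 − qs)^6 | Pass rate | P(reject H03) |
|---|---|---|---|---|
| 0 | 0 | 1 | 0.800 | 0.046 |
| 0.25 | 0.0091 | 0.9465 | 0.845 | 0.27 |
| 0.50 | 0.0183 | 0.8954 | 0.893 | 0.78 |

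The number of beats in the strip does not enter the pass rate. It only affects whether a window can be found.

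**4. A cruder check.** Suppose instead that a share g of would-be failing windows is replaced by passing ones. The pass rate becomes 0.80 + 0.20g, and P(reject) is 0.111, 0.315 and 0.833 for g = 0.10, 0.25 and 0.50. The direction and order of size agree with step 3.

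**5. Sensitivity to persistence.** If distortion comes from a cause that lasts the whole strip, another window in that strip is no better, and the gain in step 3 shrinks, to nothing at full persistence. What remains is loss of the pair. If a share e = 0.25 of would-be failures is excluded, the pass share among analysed pairs is 0.80/(0.80 + 0.20 × 0.75) = 0.842, and P(reject) with 88 analysed pairs is 0.247. The documents give no value for e either.

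**The case against.** The strongest reply is that the context gives the match condition an innocent meaning. The strips are synchronised beforehand, the worked example selects on artifact and beat number alone, and section 5.3.9 speaks of paired beats. Taking the first six consecutive beats limits discretion. The technicians are certified and do not know which strip comes from the software, so they cannot knowingly favour it. The Operations Plan/Imaging Charter cited at the head of section 5.2.1.4 may define the term.

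Most of this stands. It makes timing the likelier intent and makes deliberate favour implausible. It does not close the gap. Blinding hides identity, not disagreement between the strips. The first-six rule is neutral only if skipping is unrelated to shape, and no supplied text secures that.

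A reader might go further and infer that the plan instructs technicians to select beats on the outcome, so that H03 is bound to succeed. One could support this with a calculation: if 10% of beats mismatch independently, a fixed window passes in 0.9^6 = 53% of pairs, while a matching run of six exists somewhere in 99–100% of strips of 25 to 55 beats. The documents do not support that reading. Besides the context above, the sample size is set "under the assumption that the true population subject success rate is 90" per cent, so failures among analysed pairs are expected. The 10% rate is not in the documents. Under the same independence model, the plan's pass rates of 90% and 80% correspond to about 1.7% and 3.7% of beats (1 − 0.90^(1/6) and 1 − 0.80^(1/6)). The calculation also equates the picker's view with the majority vote.

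That the overlay precedes the selection is likewise inferred only from the order of the list. The supported point is that the text does not prevent this order.

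**Conclusion.** The concern holds as an unguarded ambiguity in the beat-selection rule, with a picker who is not independent of the scoring. It is not an instruction to select on the outcome. At a true pass rate of 80% and 88 pairs, passing over a quarter to a half of distorted beats would raise the chance of a false claim on H03 from 0.046 to between 0.27 and 0.78. These figures rest on assumed skip shares and independent beats. The effect of choosing another window is smaller if distortion persists through a strip.

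The consequence is limited to a secondary hypothesis. Objective 2a also rests on H04, and the text does not say whether the two QRS complexes measured for H04 come from the six selected beats, so no effect on H04 is claimed. If the charter already defines the selection as timing and artifact only, made before overlay, the remaining task is to carry that definition into item 19b(ii).

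**What to change.** In item 19b(ii) of the protocol and the synopsis, and in the charter:

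1. Replace the condition that beats match between the strips with: *at the same times in both strips (aligned under item 16), chosen for absence of artifact only, with each strip viewed separately before overlay*.
2. State that a readable beat whose shape differs between the strips, without noise or baseline artifact, must be kept and scored.
3. Record each beat skipped and the coded strip on which the artifact was seen. Because the technicians are blinded, the sponsor or statistician tabulates skips due to the software's strip alone after decoding.

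The cost is wording, a set order for two reading steps and a small tabulation. No extra reader is needed and the sample size is unchanged. The H03 pass rate may come out slightly less favourable. The picker would still vote, but would have chosen the beats without seeing how they overlay. A separate non-voting selector would be stricter, at the price of another reader.

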#### Study Procedures

Data collection device set up: The data collection device consists of two dry electrodes built into a smartwatch. It allows for the collection of raw single-lead ECG data that are then processed by

the software under testing (SUT) to produce a Lead-1 ECG as well as a rhythm classification of the waveform.

1. Hand subject a watch and ask subject to place it on his/her preferred wrist. Observe how the subject places the watch on their wrist.
2. Assign a device to each subject and document the device number.
3. Instruct the subject to choose his/her preferred wrist to wear the data collection device (DCD). The DCD can be worn on whichever side the subject prefers unless there is a skin condition on one wrist as noted above in the exclusion criteria, in which case, the device must be worn on the non-affected wrist. Record the subject's choice of wrist. If the subject does not have a side preference or skin condition on one wrist, the device will be placed on the left wrist.
4. Study staff will place the DCD on the study participant's wrist (as indicated in 3.) The device should be fitted tightly enough that it does not move when the hand/wrist is shaken.
5. Check band tightness for a snug fit and adjust as needed.
6. Instruct the subject to read the provided instructions on how to record a single-lead ECG. The written instructions are:
  - a) "It takes 30 seconds to record a measurement. It's important to keep your arms still. Try resting them on a table or your leg. To begin recording rest your finger on the knob."
  - b) Practice data will be recorded.
7. After the first practice run, site study staff will guide subject to appropriate study posture and grip (if not achieved independently during the first test run).
8. Allow subject up to three additional practice runs if more practice runs are needed to ensure study posture and grip instruction understanding (fewer than 3 additional practice runs are acceptable if study posture and grip are correct and subject is comfortable with the positioning),
9. Record the number of practice runs completed by the subject. First practice run data and number of practice runs completed by the subject will be used to determine ease of use.

Data collection:

10. Instruct subject to remain seated for a 5-minute resting period prior to collecting three 12-lead ECGs and set the reference system to 40 Hz filter. Use standard placement of all 12-lead electrodes (with limb lead for Lead 1).

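### Does reading R amplitude to the nearest millimetre make the 2 mm agreement limit in H04 too lenient?

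*Combined protocol and SAP*

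**What the plan says.** Section 5.2.1.4, item 19b(iv), sets the reading method for Part A: "Measure R amplitude from the isoelectric baseline to the nearest millimeter for the first two QRS complexes" in both strips. It continues: "The reviewers will be blinded to the identity of the reference strip and SUT strip. Record these lengths". The recorded data are therefore whole numbers of millimetres.

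Section 5.3.2 builds H04 on those readings. The pair is scored by majority, that is, "if at least two technicians measure the difference in amplitudes between the SUT and reference strip" as 2 mm or less. Of the two beats measured, the one with the larger R amplitude on the 12-lead is used. The parameter "represents the true population agreement proportion of paired R-Wave amplitude measurements", and the test is of 0.80 against more than 0.80. Section 5.3.5 sets a one-sided level of 0.05.

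Section 5.3.3 gives no sample size for H04. For H03, which has the same null value and level, it states that "88 subjects will provide at least 80% power to reject its null hypothesis using a one-sided type I error of 0.05" if the true rate is 90%. About 140 subjects are selected for Part A.

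**The concern.** The difference of two whole-millimetre readings is a whole number, so the inclusive limit accepts a recorded 0, 1 or 2. A pair that truly differs by, say, 2.4 mm may be recorded as differing by 2 or by 3, depending on where the two R peaks fall between grid lines. With an accurate reader, rounding never turns true agreement into disagreement, but it does turn some disagreement into agreement. The limit thus acts on average more like 2.5 mm than 2 mm.

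H04 is the only quantitative test behind objective 2a; H03 rests on a visual overlay. Someone who reads a pass as proof that more than 80% of subjects truly agree within 2 mm could be misled if true agreement were in fact 80% or somewhat lower. The plan does not spell this out.

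**Working it through.** **Inputs.** From the protocol: 1 mm reading resolution, limit of 2 mm inclusive, two-of-three majority, null 0.80, one-sided level 0.05, n=88 (H03's figure) and about 140 selected. Assumed, because the protocol does not give them: the distribution of true differences, the size of reading error, and an exact binomial test.

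**1. The plan's own figure.** With n=88, the exact test of 0.80 rejects at 77 or more passes. P(X ≥ 77 | 88, 0.80) = 0.046 and P(X ≥ 77 | 88, 0.90) = 0.833. The stated power of at least 80% for H03 is reproduced. With n=140 the rule is 121 or more, with level 0.032.

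**2. Effect of rounding on one pair.** For a true difference d and no reading error, the recorded difference is d rounded down or up, and it is rounded up with probability equal to the fractional part of d. Hence:

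- |d| ≤ 2 mm: always passes
- 2 < |d| < 3 mm: passes with probability 3 − |d| (0.75 at 2.25, 0.50 at 2.5, 0.25 at 2.75)
- |d| ≥ 3 mm: never passes

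**3. Effect on the proportion.** Scored agreement = P(|d| ≤ 2) + ∫ (3 − |d|) f(d) dd over 2 < |d| < 3. Set P(|d| ≤ 2) = 0.80.

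- Normal, mean 0: SD = 2/1.2816 = 1.561 mm. The added part is 2 × [3 × (0.9727 − 0.9000) − 1.561 × (0.1755 − 0.0629)] ≈ 0.085, so scored agreement is 0.885.
- Laplace: scale = 2/ln 5 = 1.243 mm. The added part is 0.2 × [1 − 1.243 × (1 − 0.447)] ≈ 0.063, so scored agreement is 0.863.

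**4. Chance of rejecting H04 when true agreement is exactly 80%.**

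| Differences | Scored | n=88 | n=140 |
|---|---|---|---|
| Normal | 0.885 | 0.69 | 0.82 |
| Laplace | 0.863 | 0.44 | 0.54 |
| Normal, 1 mm offset | 0.893 | 0.77 | 0.89 |
| Cauchy | 0.836 | 0.20 | 0.22 |

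Read the other way, scored agreement of 80% corresponds to true agreement of about 70% (normal) or 73% (Laplace).

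**5. Reading error.** In a simulation with normal differences, independent error on each strip and a two-of-three majority, the scored proportion with and without rounding is 0.872 against 0.780 at a reader SD of 0.5 mm, and 0.822 against 0.710 at 1 mm. Rejection at n=88 with rounding falls to 0.54 and 0.12. Reading error therefore lowers the chance of a pass, although rounding still lifts the score for the same reader.

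**6. Away from the boundary (normal, no reading error).**

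| True within 2 mm | Scored | Gain (points) |
|---|---|---|
| 80.0% | 88.5% | 8.5 |
| 90.0% | 95.5% | 5.5 |
| 95.5% (SD 1.0 mm) | 98.4% | 2.9 |
| 98.8% (SD 0.8 mm) | 99.7% | 0.9 |

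In the last three rows true agreement exceeds 80%, so a pass leads to a correct statement even on the unrounded scale.

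**7. What the test is about.** Item 19b(iv) fixes the resolution and says that the lengths are recorded; section 5.3.2 defines the proportion on those measurements. If the proportion of recorded readings that agree is 0.80, H04 is rejected with probability 0.046 (n=88) or 0.032 (n=140). The figures in step 4 answer another question: how often the test rejects when agreement of unrounded amplitudes is 80%. The plan states no such null hypothesis.

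**The case for a change.** The case for a change is that objective 2a claims clinical equivalence, that users of the result care about true amplitudes, and that a bare pass (77/88 or 121/140) is well short of what would support more than 80% true agreement within 2 mm. In the normal case without reading error that would take about 84/88 or 131/140. The digital recordings exist, and under section 5.2.1.3 "the Sponsor will sync Lead 1 of the 12-lead (reference strip) to the corresponding" SUT strip, so a finer comparison could be reported beside the technicians' result.

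The point about interpretation stands: reading error aside, a recorded agreement guarantees only a true difference below 3 mm. It does not carry through to a change in the plan, for three reasons.

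- A sentence saying that the parameter refers to whole-millimetre readings would only write down what item 19b(iv) and section 5.3.2 already say when read together. It would change no data, test or decision.
- The core lab works from PDFs that it prints (items 17 and 18). A native-resolution measurement by the core lab would need a new data transfer and a specified, validated algorithm. Reported only alongside, it would leave the H04 decision as it is.
- The documents give no reason to treat exactly 2.0 mm as a sharp boundary. A limit of 2 mm on readings taken to 1 mm is a workable convention, and statisticians could reasonably differ on whether an unrounded limit serves better.

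The Operations Plan/Imaging Charter, which may hold further reading rules, was not available.

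**Conclusion.** The arithmetic behind the concern is right, but no change to the plan is needed. H04 is a valid 5% test of the proportion it names, namely agreement of the recorded readings. The lenient zone is confined to true differences between 2 and 3 mm. It matters for interpretation only if true agreement lies near or below 80%, where normal or Laplace differences without reading error add 6 to 8.5 points to the score. At 90% true agreement the gain is 5.5 points (normal) and the conclusion is correct; with an SD of 0.8 mm it is about 1 point.

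All these sizes depend on an assumed distribution of differences and assumed reading error, since the documents give neither, and on n=88 or 140 standing in for an H04 sample size that is not stated. Whoever reports H04 can describe it as agreement of whole-millimetre readings and give the observed proportion, which shows how far above the bar the result lies.
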